5.4 Removal of Subjects from Therapy or Assessment

5.4.1 Discontinuation of Individual Subjects

Subjects can request to be discontinued from participation in the study at any time for any reason, including but not limited to disease progression or lack of response to treatment. The Investigator may discontinue any subject's participation for any reason, including an AE, safety concerns, lack of efficacy, or failure to comply with the protocol. See Section 6.1.7 for toxicity management criteria.

Subjects will be withdrawn from study drug treatment immediately if any of the following occur:

- Clinically significant abnormal laboratory results or AEs, which rule out continuation of the study drug, as determined by the Investigator or the AbbVie Therapeutic Area Medical Director.
- Serious infections (e.g., sepsis) which cannot be adequately controlled within 2 weeks by anti-infective treatment or would put the subject at risk for continued participation in the trial as determined by the Investigator.
- The Investigator believes it is in the best interest of the subject.
- The subject requests withdrawal from the study.
- Inclusion or exclusion criteria violation was noted after the subject started study drug, when continuation of the study drug would place the subject at risk as determined by the AbbVie Therapeutic Area Medical Director.
- Introduction of prohibited medications or dosages when continuation of the study drug would place the subject at risk, as determined by the AbbVie Therapeutic Area Medical Director.

- Subject is non-compliant with TB prophylaxis (if applicable) or develops active TB at any time during the study.
- The subject becomes pregnant while on study drug.
- Malignancy, except for localized NMSC or carcinoma in-situ of the cervix.
- Subject is significantly non-compliant with study procedures which would put the subject at risk for continued participation in the trial as determined by the Investigator.
- Subject develops a gastrointestinal perforation (other than due to appendicitis or mechanical injuries).
- Confirmed diagnosis of deep vein thrombosis, pulmonary embolus or non-cardiac, non-neurologic arterial thrombosis.
- Starting at Week 24, at least 20% improvement in BOTH SJC AND TJC compared to baseline is required to remain on study drug. Anyone who does not fulfill this criterion at 2 consecutive visits (starting at Week 24) must be discontinued from study drug.

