AST or ALT	
 • Interrupt study drug immediately if confirmed ALT or AST > 3 × ULN by repeat testing with new sample and either a total bilirubin > 2 × ULN or an international normalized ratio (INR) > 1.5. 
 ○ A separate blood sample for INR testing will be needed to measure INR at the time of repeat testing for ALT or AST. A repeat test of INR is not needed for determination if above toxicity management criteria are met. • Interrupt study drug immediately if confirmed ALT or AST > 3 × ULN by repeat testing with new sample along with appearance of fatigue, nausea, vomiting, right upper quadrant pain or tenderness, fever, rash, and/or eosinophilia (> 5%). • Interrupt study drug immediately if confirmed ALT or AST > 5 × ULN by repeat testing with new sample for more than 2 weeks. • If ALT or AST > 8 × ULN, interrupt study drug immediately, confirm by repeat testing with a new sample, and contact the TA MD. 
Subjects who meet any of the above criteria should be evaluated for an alternative etiology of the ALT or AST elevation and managed as medically appropriate. If applicable, the alternative etiology should be documented in the eCRF. If ALT or AST values return to the normal reference range or its Baseline value, study drug may be restarted. If restarting study drug, documentation should include reason that rechallenge is expected to be safe. If after clinically appropriate evaluation, no alternative etiology for ALT or AST elevation is found or the ALT or AST elevation has not resolved or is not trending down toward normal, the subject should be discontinued from study drug.
 
 • For subjects with HBc Ab+ (irrespective of HBs Ab status) and negative HBV DNA at screening who develop the following should have HBV DNA by PCR testing performed within one week: 
 ○ ALT > 5 × ULN OR ○ ALT or AST > 3 × ULN if an alternative cause is not readily identified. ○ A positive result for HBV DNA PCR testing in these subjects will require immediate interruption of study drug and a hepatologist consultation should occur within one week for recommendation regarding subsequent treatment. 
For any confirmed ALT or AST elevations > 3 ULN, complete supplemental hepatic eCRF.

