#### **9.1.2 Definition of Missing Data Imputation**

##### **Non-Responder Imputation (NRI) Approach**

The NRI approach will categorize any subject who has missing value for categorical variables at a specific visit as non-responder for that visit. In addition, subjects who prematurely discontinue from study drug will be considered as non-responders for all subsequent visits after discontinuation.

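### Table 7 both allows restart and directs discontinuation when ALT/AST has returned to normal or Baseline and no alternative cause is found

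*Protocol*

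**What the plan says.** The AST or ALT row of Table 7 (Protocol 6.1.7) has four criteria for interrupting study drug:

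- confirmed ALT or AST above 3 × ULN with total bilirubin above 2 × ULN or INR above 1.5;
- confirmed ALT or AST above 3 × ULN with listed symptoms or eosinophilia;
- confirmed ALT or AST above 5 × ULN for more than two weeks;
- ALT or AST above 8 × ULN.

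One paragraph then covers all four: "Subjects who meet any of the above criteria should be evaluated for an alternative etiology of the ALT or AST elevation".

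The same paragraph gives two outcomes.

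- **Restart.** "If ALT or AST values return to the normal reference range or its Baseline value, study drug may be restarted". The one condition attached is "If restarting study drug, documentation should include reason that rechallenge is expected to be safe".
- **Discontinuation.** "If after clinically appropriate evaluation, no alternative etiology for ALT or AST elevation is found or the ALT or AST elevation has not resolved", which continues directly "or is not trending down toward normal, the subject should be discontinued from study drug".

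Protocol 5.4.1 has a general withdrawal clause for "Clinically significant abnormal laboratory results or AEs, which rule out continuation of the study drug, as determined by the Investigator" or by the sponsor's medical director. It does not mention the ALT/AST paragraph.

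**The concern.** The restart sentence looks only at the enzyme values. The discontinuation sentence looks first at the cause, and its triggers are alternatives, so an unexplained elevation is enough by itself. Nothing links the two sentences or says which prevails. An investigator with a patient whose values have normalised off drug and whose work-up is negative can find support for either action.

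The paragraph also applies to the criterion that combines raised aminotransferases with raised bilirubin or INR. SAP 10.3.2.4 treats aminotransferase abnormality with bilirubin above 2 × ULN, without biliary obstruction or another explanation, as a signal of potential for severe drug-induced liver injury. In this row only the 8 × ULN criterion calls for contact with the sponsor's medical director, so the bilirubin/INR criterion has no stated sponsor check before restart. With about 230 sites planned, uneven handling is foreseeable. It would carry into the tables of treatment-emergent adverse events leading to discontinuation (SAP 10.2.2.1 and 10.2.2.2) and into the exposure time in their denominators.

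**Working it through.** The plan gives no figure to reproduce, so the check is to apply both sentences to each situation a subject can be in.

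Inputs, all from the Table 7 paragraph:

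- Restart is open if values have returned to normal or Baseline and a reason for expecting safe rechallenge is documented.
- Discontinuation is directed if no cause is found, **or** the elevation has not resolved, **or** it is not trending down.
- Assumption: *resolved* in the second sentence means the same as the return to normal or Baseline in the first. The paragraph does not define it.

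| Alternative cause | Enzyme course | Restart sentence | Discontinuation sentence | Result |
|---|---|---|---|---|
| Found | Returned | Open | Not triggered | One instruction |
| Found | Not returned | Not open | Triggered (not resolved) | One literal instruction |
| Not found | Not returned | Not open | Triggered (two limbs) | One instruction |
| Not found | Returned | Open | Triggered (no cause) | **Both apply** |

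One of the four combinations is in conflict.

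Next, does anything else in the protocol settle that combination?

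- *Section 5.4.1* leaves laboratory abnormalities to judgement and does not rank the two sentences.
- *Section 5.5.4* and the interruption rules after Table 7 deal with the length of an interruption (7 consecutive days up to Week 24, 30 days afterwards). They do not mention cause.
- *The text introducing Table 7* refers to standard of care and local guidelines, without a tie-breaker.
- *The hemoglobin row* of the same table separates a fall without an alternative etiology from one with a known etiology. The protocol can state the dependence on cause when it means to; the ALT/AST restart sentence does not.

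Two wording points in the paragraph add to the uncertainty.

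1. An elevation that is not trending down has, by definition, not resolved. Every case caught by the trend limb is already caught by the limb before it, so with the two joined by *or* the trend limb adds nothing. Read literally, a subject with a known cause and falling but still raised values is to be discontinued.
2. The restart sentence speaks of ALT or AST values returning. If both were raised and only one has returned, the text does not say whether restart is open.

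**The case against.** The best defence is that the sentences can be read in sequence. Restart is a permission and discontinuation is a direction, so a site that discontinues breaches neither. The paragraph asks for the work-up first, and its last sentence starts from the completed evaluation, so it may have been meant to limit the earlier permission. Table 7 is also headed as guidelines. This reading is possible, but the text does not state it, and the requirement to justify rechallenge fits restart in an unexplained case equally well. A site that restarts follows one sentence and departs from the other.

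A reader might infer more than this. The documents do not support the following:

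- **That the trial's primary result is at risk.** Under SAP 9.1.2, "subjects who prematurely discontinue from study drug will be considered as non-responders for all subsequent visits after discontinuation", so a restart-or-stop decision could have changed Week 12 status. But SAP 11.1 says Period 1 reporting was completed under SAP version 2.0, and SAP Appendix B dates this to 2017. An amendment now cannot alter it. Nor do the documents show that this wording was in force during Period 1. Long-term efficacy is analysed on As Observed data, where this rule does not apply.
- **That the comparison of 15 mg with 30 mg is distorted from here on.** Since Amendment 6 all subjects receive open-label 15 mg, so future decisions cannot bias a concurrent dose comparison.
- **That the two wording points are further contradictions.** A known cause with falling values gets one literal instruction, even if an odd one. ALT or AST may simply mean whichever enzyme was raised. Both are ambiguities.
- **That permanent discontinuation of a drug-related case is required.** The text says should, where the malignancy and thrombosis rules in the same section say must. It does not say permanently, and it speaks of no alternative etiology, not of a suspected drug effect.

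**Conclusion.** The point stands in a limited form. For one of four combinations (enzymes returned, no alternative cause found) the paragraph permits restart and directs discontinuation, and no other section resolves it. This holds for all four interruption criteria. It rests on the plain wording and on reading resolved as returned to normal or Baseline.

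The live effect is on Period 2: possible inconsistency between sites in whether a patient with an unexplained liver signal is re-exposed, and hence in the counts of adverse events leading to discontinuation. Restart is a realistic event there, because interruptions of up to 30 consecutive days are allowed after Week 24 and the investigator decides on restart beyond that.

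The number of subjects affected cannot be derived. The protocol calls the Phase 2 liver test elevations sporadic, and neither document gives a rate for the Table 7 criteria, for normalisation, or for negative work-ups. A count of everyone meeting any criterion would overstate the problem, since only those who both normalise and have no cause found meet the conflict. The case for correction is patient safety and consistent conduct, not a demonstrated effect on results.

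**What to change.** The sponsor's medical team should reconcile the restart and discontinuation sentences in the AST or ALT row so that each combination of etiology finding and enzyme course leads to one instruction, including the combination in which values have returned and no cause is found. The same edit should clarify how the not-resolved and not-trending-down clauses relate, and whether ALT, AST or both must have returned. Which rule is right is for the sponsor to decide; this review does not propose one.

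The cost is a rewording of one table cell in the next amendment, with the ethics committee approval that Protocol 9.1 requires for amendments, and a letter to sites. No new tests, visits or analyses are needed. The current amendment already revised this row for the 8 × ULN criterion.

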6.1.8 Data Monitoring Committee

An external DMC will review unblinded safety data. See Section [5.5.5.2](#) for details.

6.1.9 Cardiovascular Adjudication Committee

An independent committee of physician experts in cardiovascular adjudication will be utilized to assess potential cardiovascular AEs in a blinded manner as defined by the Cardiovascular Adjudication Committee charter.

6.2 Product Complaint

6.2.1 Definition

A Product Complaint is any Complaint (see Section [6.0](#) for the definition) related to the biologic or drug component of the product.

For a product this may include, but is not limited to, damaged/broken product or packaging, product appearance whose color/markings do not match the labeling, labeling discrepancies/inadequacies in the labeling/instructions (example: printing illegible), missing components/product, or packaging issues.

Any information available to help in the determination of causality to the events outlined directly above should be captured.

6.2.2 Reporting

Product Complaints concerning the investigational product must be reported to the Sponsor within 24 hours of the study site's knowledge of the event via the Product Complaint form. Product Complaints occurring during the study will be followed-up to a satisfactory conclusion. All follow-up information is to be reported to the Sponsor (or an authorized representative) and documented in source as required by the Sponsor. Product

Complaints associated with adverse events will be reported in the study summary. All other complaints will be monitored on an ongoing basis.

Product Complaints may require return of the product with the alleged complaint condition. In instances where a return is requested, every effort should be made by the Investigator to return the product within 30 days. If returns cannot be accommodated within 30 days, the site will need to provide justification and an estimated date of return.

The description of the complaint is important for AbbVie in order to enable AbbVie to investigate and determine if any corrective actions are required.

8.0 Statistical Methods and Determination of Sample Size

8.1 Statistical and Analytical Plans

An unblinded analysis will be conducted after all subjects have completed Period 1 (Week 12) for the purpose of regulatory submission. Study sites and subjects will remain blinded for the duration of the study.

Completed and specific details of the statistical analysis will be described and fully documented in the Statistical Analysis Plan (SAP). The SAP will be finalized prior to the database lock for the analysis at the end of Period 1. The statistical analyses will be performed using SAS (SAS Institute Inc., Cary, NC, USA).

Starting with Amendment 6, all subjects will receive open-label upadacitinib 15 mg QD, including those currently on upadacitinib 30 mg QD. The details for handling the change in dose in analysis will be described in the Statistical Analysis Plan (SAP) for final reporting.

8.1.1 Analysis Populations

8.1.1.1 Full Analysis Set (FAS)

The Full Analysis Set (FAS) includes all randomized subjects who received at least one dose of study drug. The FAS will be used for all efficacy and baseline analyses.

8.1.1.2 Per Protocol Analysis Set

The Per-Protocol Analysis Set represents a subset of the FAS and consists of all FAS subjects who did not meet any major protocol violations during the study. Definitions of major protocol violations will be detailed in the SAP. Additional analysis may be conducted on the Per Protocol analysis set, in order to evaluate the impact of major protocol violations.

8.1.1.3 Safety Analysis Set

The Safety Analysis Set consists of all subjects who received at least one dose of study drug. For the Safety Analysis Set, subjects are assigned to a treatment group based on the treatment actually received, regardless of the treatment randomized.

8.1.2 Subject Accountability, Disposition and Study Drug Exposure

8.1.2.1 Subject Accountability

The following will be summarized by site and by treatment group as well as overall, separately for Period 1 and Period 2: number of subjects randomized, the number of subjects who received at least one dose of study drug, the number of subjects who completed, the number of subjects who prematurely discontinued study drug, and the number of subjects who prematurely discontinued study participation.

8.1.2.2 Subject Disposition

Separately for Period 1 and Period 2, the number and percentage of subjects who are randomized, received at least one dose of study drug, prematurely discontinued study

drug, prematurely discontinued study participation, and completed will be summarized by treatment group and overall. Reasons for premature discontinuation of study drug and study participation will be summarized separately for all randomized subjects by treatment group and overall, with frequencies and percentages by reason for discontinuation.

8.1.2.3 Study Drug Exposure

Exposure to study drug will be summarized for the Safety Analysis Set for Period 1 alone as well as for Period 1 and Period 2 combined. The exposure to study drug (days) will be summarized with the mean, standard deviation, median, and range for each treatment group. The exposure to study drug is defined as the difference between the dates of the first and last doses of the study drug plus 1 day.

Study drug compliance will be summarized for each treatment group for Period 1. The compliance is defined as the number of tablets taken (i.e., the difference between the number of tablets dispensed and the number of tablets returned) during the subject's participation in Period 1 divided by the number of tablets a subject is supposed to take each day times the length of time that the subject was in the Treatment Phase of Period 1.

8.1.3 Analysis of Demographic and Baseline Characteristics

Demographic and baseline characteristics will be summarized by treatment group and overall for the FAS. For the purpose of this analysis, baseline data for each subject will be the data collected immediately prior to the first dose of study drug in Period 1.

Summary statistics for continuous variables will include the number of observations, mean, standard deviation, median, and range. For discrete variables, frequencies and percentages for each category will be summarized.

Medical history will be presented by counts and percentages of subjects, broken down by Body System and Diagnosis.

Prior therapy and medication will be summarized by treatment group. Prior therapy and medication will include all therapies and medications with a start date prior to the date of first dose of study drug.

Concomitant medications will also be summarized with frequencies and percentages for each treatment group. All medications administered during study drug exposure will be included.

8.1.4 Efficacy Analysis

All efficacy analyses will be carried out using the FAS population, which includes all randomized subjects who receive at least one dose of study drug.

8.1.4.1 Efficacy Analysis for Period 1

For all efficacy analysis in Period 1, the two placebo groups (Groups 3 and 4) will be combined and treated as one placebo group for analysis purposes. Each upadacitinib dose will be compared with the combined placebo group.

8.1.4.1.1 Primary Efficacy Variables

The primary endpoint in Period 1 (at Week 12) for US/FDA regulatory purposes is listed in Section 5.3.3.1.1. The primary endpoint in Period 1 (at Week 12) for EU/EMA regulatory purposes is also listed in Section 5.3.3.1.1. Analyses will be conducted separately for US/FDA regulatory purposes and EU/EMA regulatory purposes; for each set of analyses, only one primary endpoint is specified.

Analysis of the primary endpoint will be conducted on the FAS based on treatment as randomized. Comparison of the primary endpoint will be made between each upadacitinib group and the combined placebo groups using the Cochran-Mantel-Haenszel test adjusting for main stratification factors. For the primary analysis, Non-Responder Imputation (NRI) will be used. The analysis will be repeated using Observed Cases (OC). Supportive analysis will also be conducted on the Per Protocol Analysis Set.

The primary efficacy analyses will also be performed in demographic subgroups including age, gender, weight, body mass index, race, and geographical region to assess the consistency of the treatment effect. Additional subgroup analyses based on baseline disease characteristics and stratification factors will also be conducted.

8.1.4.1.2 Key Secondary Efficacy Variables

Key secondary endpoints (at Week 12) for US/FDA regulatory purposes are listed in Section 5.3.3.1.2. Key secondary endpoints in (at Week 12) for EU/EMA regulatory purposes are also listed in Section 5.3.3.1.2.

For binary endpoints, frequencies and percentages will be reported for each treatment group. Similar analyses as for the primary endpoint will be conducted.

For continuous endpoints, the mean, standard deviation, median, and range will be reported for each treatment group. Pairwise comparisons for each of the upadacitinib treatment groups and the combined placebo groups will be carried out using the analysis of covariance model with treatment group as the fixed factor, and the corresponding baseline value and the main stratification factors as the covariates.

See Section 8.1.4.1.5 for imputation methods.

8.1.4.1.3 Other Efficacy Variables

Additional efficacy variables are listed in Section 5.3.3.1.3 and will be summarized for all visits. For binary endpoints, frequencies and percentages will be reported for each treatment group. For continuous endpoints, the change from baseline mean, standard deviation, median, and range will be reported for each treatment group.

8.1.4.1.4 Multiplicity Control for the Primary and Key Ranked Secondary Endpoints

The overall type I error rate of the primary and ranked key secondary endpoints for the two doses will be strongly controlled using a graphical multiple testing procedure.²³

Specifically, the testing will utilize the endpoint sequence of primary endpoint followed by the ranked key secondary endpoints, and will begin with testing the primary endpoint using α of 0.025 for each dose. Continued testing will follow a pre-specified α transfer path which includes downstream transfer along the endpoint sequence within each dose as well as cross-dose transfer. More details of the graphical procedure will be specified in the SAP.

